More than 60,000 infants are born between 22 to 32 weeks gestation age (very or extremely premature) annually in the US. Approximately 11% of them develop comorbidities, i.e., oral feeding difficulty, failure to thrive, delayed neurodevelopment, and maladapted parent-infant interaction. As part of the Neonatal Intensive Care Unit (NICU) hospitalization, very and extremely preterm infants inevitably endure early life toxic stress, e.g., parental separation, painful procedures, sleep fragmentation, harmful hospital organisms, and antibiotic therapy, without adequate protective buffers. Early life toxic stress results in adverse epigenetic modifications of glucocorticoid-related genes (DNA methylation of NR3C1 and HSD11B2) and dysbiosis (altered gut microbiome), both impairing neurodevelopment. These adversities further exacerbate the risk of comorbidities and inappropriate brain development during sensitive periods of neuroplasticity. Evidence suggests adverse epigenetic modifications and dysbiosis may set a life-long trajectory of risk for chronic health conditions, i.e., mental health disorders, cardiometabolic and immunologic diseases. Hence, it is a clinical and scientific priority to test an early NICU intervention to attenuate stress-related adverse epigenetic modifications and dysbiosis. Prior research has paved the way for a potential early NICU intervention as follows. Human milk influences the structure and relative abundance of healthy gut bacteria, i.e., short-chain fatty acid (SCFA)- and lactate-producing bacteria (e.g., *Bifidobacterium* and *Lactobacillus*), and neurodevelopment. Maternal nurturing, e.g., licking and grooming (in rodents), and breastfeeding and touch (in humans), promotes neurodevelopment, reduces stress, and reverses stress-related epigenetic modifications. Building on what is known, the multisensory early oral administration of human milk (M-MILK) intervention by nurses or parents is designed to provide an enjoyable and nurturing experience for infants, through a safe and consistent infant-guided provision of human milk droplets, given orally as early as 22 weeks postmenstrual age. M-MILK is implemented after every hands-on care and during the beginning of a full gavage feeding. The objective of our planned NIH R01 randomized controlled trial is to examine the efficacy of M-MILK from birth to 2 months corrected age, and the mechanisms whereby this may occur. We propose the M-MILK pilot study (N = 20): a 2-group, 10 per group, parallel design, and longitudinal randomized controlled trial in preterm infants who are born between 22 to 33 weeks gestational age. M-MILK will begin on day 3 of life. We will measure outcomes using validated methodologies: maternal postpartum depressive symptoms via the Edinburgh Postnatal Depression Scale, parent stress via the Parental Stressor Scale: NICU, parent discharge readiness via the Screening and Multi-disciplinary Risk Assessment Scale & Parent Activation Scale, neurodevelopment via the Neurobehavioral Assessment of the Preterm Infants and Ages & Stages Questionnaire-3, oral feeding skills via the Early Feeding Skills Assessment and NeoEAT, parent-infant interaction during feeding via the Nursing Child Assessment Satellite Training-Feeding Scale and Postpartum Bonding Questionnaire, DNA methylation of NR3C1 and HSD11B2 via buccal samples, and gut microbiome via fecal samples. Outcomes will be measured at baseline, 34 weeks postmenstrual age, discharge, and 2 months corrected age. The aims of this pilot study are to (1) determine the feasibility and acceptability of the M-MILK intervention by nurses and parents, (2) determine the feasibility of recruitment and retention, (3) obtain variability data for sample size estimation, and (4) evaluate the charges and costs of the NICU hospitalization and 2 months CA care between the M-MILK and control groups. M-MILK will be considered feasible if M-MILK is implemented by nurses or parents after every hands-on care and during the beginning of a full gavage feeding at least 90% of the time. The M-MILK acceptability by nurses and parents will be determined via M-MILK Acceptability Questionnaire. Recruitment and retention will be considered feasible if at least 50% of infants approached for participation enrolled, 90% of infants completed all inpatient data collection, and at least 50% of infants completed post-discharge follow-ups. This pilot study will inform our R01 application regarding the feasibility and acceptability of M-MILK and sample size estimation.

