The M-MILK pilot study ($N = 12$) is a 2-group, 6 per group, parallel design, and longitudinal randomized controlled trial. We will recruit preterm infants who are born between 22 to 33 weeks gestational age. We will compare the outcomes between the M-MILK and attention control groups. Infants will be enrolled into the study as soon as possible after they are admitted to the NICU. If infants are in the M-MILK group, M-MILK will begin on day 3 of life after every hands-on care and during the beginning of a full gavage feeding. We will measure outcomes using validated methodologies at baseline (enrollment), 34 weeks PMA, discharge, and 2 months CA.

b. Setting

The M-MILK pilot study will be conducted in a level III NICU at LUMC (Maywood, IL). The hospital provides care to families with diverse racial, ethnic, and socioeconomic backgrounds. The nursing staff are predominantly registered nurses and advanced nurse practitioners, and the physicians are board certified

neonatologists. Infants are fed using mother's own milk, donor milk, and/or formula. However, we will only include infants who receive mother's own milk or donor's milk.

c. Sample

We will enroll 12 preterm infants (6 per group). Anticipated a 40% attrition rate, we expect the final sample size to be 12 preterm infants. Estimates of average values and variability of continuous measures are acceptable at this sample size using the "rule of 12" as recommended.³¹

VII. Study Procedures

a. Subject Selection Procedures

i. Inclusion/Exclusion Criteria

Inclusion criteria

- Born between 22 to 33 weeks gestational age
- Mother is pumping and infant is receiving mother's own milk and/or donor's milk to be in the intervention group.

Exclusion criteria

- Congenital abnormalities in the digestive, e.g., clef lip and palate, omphalocele
- Necrotizing enterocolitis
- Congenital heart disease that requires surgery

ii. Screening procedures

After infants are admitted to the NICU, we will review their electronic medical records to screen for eligible infants according to the inclusion and exclusion criteria. Once an infant is enrolled into the study, the screening period continues until NICU discharge. The infant will be classified as screen failed and excluded if he/she develops any of the exclusion criteria.

iii. Recruitment Procedures

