
	continuous measure based on total percent of methylation for each NR3C1 and HSD11B2 promoter region as well as for each individual CpG site.	
Gut Microbiome	
Infant fecal samples will be collected by a bedside nurse in the NICU at baseline, 34 weeks PMA, NICU discharge. For the 2 months CA sample, parents will receive a fecal collection kit with written instructions to collect and send samples to our lab via USPS postal services.
 
Fecal samples from each infant will be collected using sterile, disposable spatulas during diaper changes and then placed into a sterile specimen container with microbial DNA stabilizer solution for 60 days at room temperature. The samples collected will be transported to a laboratory at the Loyola University Chicago Center for Translational Research and Education (Maywood, IL). All samples will be stored at room temperature. Monthly, the buccal swab samples will be securely transported in a biospecimen transfer container (Saf T Pak, Austell, GA) via car to Rush University Medical Center Genomics and Microbiome Core Facility (Chicago, IL) for processing and analyses. Genomic DNA will be extracted from fecal material using a Maxwell RSC48 autM-MILKted extraction device (Promega) and employing a Maxwell RSC Fecal Microbiome DNA kit, as described previously.⁶⁴ Samples will be subject to physical shearing (i.e., bead-beating) using a TissueLyser II device (Qiagen) prior to extraction. Genomic DNA will be prepared for sequencing using a two-stage amplicon sequencing workflow⁶⁵ and employing primers 515F-modified and 806r-modified.⁶⁶ Sequencing will be performed a MiniSeq sequencer (Illumina)⁶⁴ with paired-end 2x154 base sequencing. Basic processing of sequence data, including merging of forward and reverse reads, quality and primer trimming, chimera removal, and selection and annotation of amplicon sequence variants (ASVs) will be performed.⁶⁴ Alpha diversity indices (e.g., Shannon index) will be calculated on rarefied datasets⁶⁷ in R using the vegan library package.⁶⁸ Pairwise comparisons of alpha diversity indices will be performed using the non-parametric Mann–Whitney test. Beta diversity analyses will be performed on pairwise Bray–Curtis indices calculated in R using the metaMDSdist function in the vegan library v2.5-6. The dissimilarity indices will be modelled and tested for significance with the sample covariates using PERMANOVA.⁶⁹ Differential abundance analyses of individual taxa between groups will be performed using the software package DESeq2, generating an FDR q-value.⁷⁰ DESeq2 has been shown to be appropriate for differential abundance comparisons in studies with small sample size groups (< 20) or unbalanced design.⁷¹ To identify taxa that most strongly explain between-group differences, a Linear discriminant analysis Effect Size (LEfSe) analysis will performed.⁷¹
	T0, T1, T3, T4 Fecal samples

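### LEfSe is planned to name the taxa behind the arm difference with no stated multiplicity control and no stated link to the DESeq2 q-values from the same samples

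*Combined protocol and SAP*

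**What the plan says.** All of the microbiome analysis is in section VII.a.vi.1 (Measures), Table 1, Gut Microbiome row. Sequences are processed to the point where "selection and annotation of amplicon sequence variants (ASVs) will be performed". Alpha diversity is compared by Mann–Whitney tests, and Bray–Curtis dissimilarities are tested by PERMANOVA.

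Two taxon-level analyses follow:

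- "Differential abundance analyses of individual taxa between groups will be performed using the software package DESeq2, generating an FDR" q-value. No q cut-off is given.
- "To identify taxa that most strongly explain between-group differences, a Linear discriminant analysis Effect Size (LEfSe) analysis will performed".

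For LEfSe the documents give no significance level, effect-size cut-off, correction across taxa, taxonomic level, prevalence filter or visit. They do not say how its list relates to the DESeq2 q-values. Section IX (Data Management and Analysis Plan) adds nothing on the microbiome or on multiplicity. Fecal samples are taken at T0, T1, T3 and T4.

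The arm size is stated in two ways. Section VI.a says the trial "is a 2-group, 6 per group, parallel design, and longitudinal randomized controlled trial", while the opening summary says "We propose the M-MILK pilot study (N = 20): a 2-group, 10 per group".

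**The concern.** The plan recognises that testing many taxa needs error control and provides it for DESeq2. It then gives the job of picking out the taxa responsible for the arm difference to a second search of the same samples, for which no control is stated. FDR control of the DESeq2 list does not carry over to a list produced by another method. The LEfSe sentence also takes for granted that there is a difference to explain.

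Suppose DESeq2 finds nothing and LEfSe lists three taxa. The plan does not say which result stands. With six infants per arm, such a list could consist wholly of chance findings. The pilot feeds an R01 application concerned with mechanisms, and the Background already names *Bifidobacterium* and *Lactobacillus*, so a chance list could be read as support for a mechanism.

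**Working it through.** The plan gives no error rate for LEfSe, so there is no figure to reproduce. The check asks how often one LEfSe run would name at least one taxon if M-MILK had no effect.

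**From the documents.** The arms are 6 vs 6 (section VI.c: "We will enroll 12 preterm infants (6 per group") or 10 vs 10 (opening summary). Section VI.c also says: "Anticipated a 40% attrition rate, we expect the final sample size to be 12 preterm infants". Since 12 × 0.6 = 7.2 and 20 × 0.6 = 12, twelve completers match 20 enrolled, not 12. If 12 are enrolled and 40% are lost, about 4 vs 3 remain.

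**Assumed, because the documents are silent.** LEfSe screens each taxon by an uncorrected rank test at level 0.05 (range 0.01 to 0.05) and may then apply an effect-size cut-off on a log10 scale: none, 2 (lenient) or 4 (strict). The number of taxa m runs from 10 to 100.

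**Step 1: actual level of the rank test.** At 6 vs 6 there are C(12,6) = 924 equally likely rank allocations. The Kruskal–Wallis chi-square p is below 0.05 for 38 of them, so the exact level is 38/924 = 0.0411. It is 0.0524 at 10 vs 10 and 0.0571 at 4 vs 3.

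**Step 2: chance of at least one false name.** For m independent taxa at level a, this is 1 − (1 − a)^m. For example, at 6 vs 6 with 17 taxa, 1 − 0.9589^17 = 0.51.

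**Step 3: simulation.** Real taxa are correlated and sparse, so compositional, zero-inflated, block-correlated counts were simulated with no arm effect, 300 runs per setting (standard error at most √(0.25/300) ≈ 0.03). A scaled mean difference stood in for the LEfSe score.

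Results for one run at 6 vs 6:

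| m | formula, 0.05 | formula, exact 0.0411 | simulated, no cut-off or 2 | simulated, cut-off 4 | formula, 0.01 |
|---|---|---|---|---|---|
| 10 | 40% | 34% | 31–37% | 22–27% | 10% |
| 17 | 58% | 51% | not run | not run | 16% |
| 20 | 64% | 57% | 56–62% | 31–39% | 18% |
| 50 | 92% | 88% | 84–88% | 45–51% | 39% |
| 100 | 99% | 98% | 97–99% | 44–54% | 63% |

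For 17 to 20 taxa, the exact level and the simulation together give 51 to 62%; the nominal 0.05 formula takes the top of the range to 64%. The 50% mark is passed at 14 taxa at nominal 0.05 (1 − 0.95^14 = 0.51), at 17 with the exact 6 vs 6 level, and only at 69 if the level is 0.01 (1 − 0.99^69 = 0.50).

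**Step 4: does arm size matter?** Little. With 20 taxa at 10 vs 10, 1 − 0.9476^20 = 0.66. At 4 vs 3, with no cut-off or cut-off 2, the simulation gave 54 to 70% with 20 taxa and 84 to 93% with 50.

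**Step 5: would correcting the LEfSe rank tests themselves work?** Benjamini–Hochberg at 0.05 on the same p-values cut false lists to 0 to 3% at 6 vs 6 and 0% at 4 vs 3, but at a heavy price. The smallest attainable p at 6 vs 6 is 0.0039, so a lone taxon can pass only if 0.05/m ≥ 0.0039, that is, m ≤ 12. At 4 vs 3 the smallest p is 0.034, so a lone taxon passes only if m = 1.

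**The case against.** The strongest reply is that the row already controls error where it matters. DESeq2 is the analysis labelled as differential abundance and carries FDR q-values, and PERMANOVA tests for a community-level difference. The plan does not depend on LEfSe to decide whether M-MILK changed the microbiome. The LEfSe sentence comes after these tests and can be read as a ranking by effect size. This stands as a limit on the consequence. It does not close the gap, because nothing in the text restricts LEfSe to taxa that pass DESeq2.

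A second reply is that no decision rests on the list. None of the four aims or the feasibility criteria in section IV uses differential taxa, and the opening summary says the pilot informs the R01 on feasibility, acceptability and sample size. This also stands. A reader might infer that a false list would corrupt the go decision, but the documents do not support that.

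A reader might also infer that LEfSe would name a taxon in most null analyses whatever the settings. The documents do not support this either: the level, number of taxa and cut-off are all unstated, and parts of the plausible range fall well below one half. Nor do they say that LEfSe is run at every visit, so compounding the error over four visits would be a further assumption.

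**Conclusion.** The point holds in a limited form. The plan has LEfSe name taxa as accounting for the arm difference without stated multiplicity control and without tying that list to the q-values it already computes. Under the assumed uncorrected rank test at 0.05 with a lenient cut-off, the false-list rate per run far exceeds 5% at every taxon count examined, and it passes one half from roughly 14 to 17 effectively independent taxa. A strict cut-off or a level of 0.01 lowers it substantially, though still not to 5% in the settings examined. The size therefore depends on choices that the plan leaves open and that could be made after the data are seen.

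It would be wrong to conclude that the taxon-level plan has no error control, since DESeq2 supplies it. What is at stake is the credibility of exploratory microbiome reporting, not the pilot's feasibility conclusions. The change is worth making because the remedy uses output already planned.

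**What to change.** Replace the LEfSe sentence in Table 1 with a rule along these lines: a taxon is named as differing between arms only if its DESeq2 FDR q-value is below 0.05 at that visit; LEfSe scores are shown as an exploratory effect-size ranking with the DESeq2 q-value beside each taxon; if no taxon passes, the report says that none was identified. For the two columns to match, both analyses need the same taxonomic level and filter.

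Benjamini–Hochberg on the LEfSe rank-test p-values should not be offered as an alternative. It is close to unusable at this sample size, and a choice between two criteria would reopen the ambiguity.

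The cost is one sentence and no new data. The downside is that fewer taxa, possibly none, will be named at this sample size.

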The aims of this pilot study are to (1) determine the feasibility and acceptability of the M-MILK intervention by nurses and parents, (2) determine the feasibility of recruitment and retention, (3) obtain variability data for sample size estimation, and (4) evaluate the charges and costs of the NICU hospitalization and 2 months CA care between the M-MILK and control groups. M-MILK will be considered feasible if M-MILK is implemented by nurses or parents after every hands-on care and during the beginning of a full gavage feeding at least 90% of the time. The M-MILK acceptability by nurses and parents will be determined via M-MILK Acceptability Questionnaire. Recruitment and retention will be considered feasible if at least 50% of infants approached for participation enrolled, 90% of infants completed all inpatient data collection, and at least 50% of infants completed post-discharge follow-ups.

V. Administrative Organization

Participants will be enrolled in the Neonatal Intensive Care Unit (NICU) at Loyola University Medical Center (LUMC) (Maywood, IL). The inpatient components of the study protocol will be conducted in the NICU at LUMC. The post-discharge follow-up components of the study protocol will be conducted via phone/zoom interview. Data storage and management will be carried out via REDCap (version 10.4.0, Vanderbilt University) and a secured research network drive, hosted by the Loyola University Chicago (Maywood, IL).

Upon sample collection, buccal swab and fecal samples will be labeled only with study ID numbers and collection date, and stored in a locked cabinet in a locked laboratory at Loyola University Chicago (LUC) Center for Translational Research and Education (CTRE). All samples will be stored at room temperature. Quarterly, the buccal swab samples and fecal samples will be securely transported in a biospecimen transfer container (Saf T Pak, Austell, GA) via car to Rush University Medical Center Genomics and Microbiome Core Facility (Rush) (Chicago, IL) for processing and analyses. A Service Agreement between LUC and Rush will be submitted through LUC Research Portal.

VI. Study Design

a. Design

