Charges and costs of care	Healthcare use and associated charges and costs of the NICU hospitalization and 2 months CA care will be extracted from LUMC's electronic health and billing records. For infants receiving care outside LUMC 2 months CA, we will ask the parents about the extent and types of healthcare received outside LUMC. We will evaluate healthcare use, costs, and charges between the M-MILK and control groups. We will also describe the extent and types of healthcare use 2 months CA for infants receiving care outside LUMC at discharge. In the R01 trial, we will use activity-based costing approach to calculate the time and resources costs of delivering the M-MILK intervention by nurses and parents (which may not be fully reflected in the health system billing records), and query NICU hospitalization and 2 months CA healthcare use, charges, and costs to calculate total benefits and costs of M-MILK Intervention vs. control group.	T3 & T4
M-MILK Acceptability Questionnaire	The M-MILK Acceptability Questionnaire will be completed by parents at discharge. The nurses will complete the M-MILK Acceptability Questionnaire at the end of the entire study.	T3 M-MILK Acceptability Questionnaire

Note. EPIC = electronic medical record; GA = gestational age; PMA = postmenstrual age; CA = corrected age; Ongoing = throughout hospitalization from enrollment to discharge; T0 = baseline; T1 = 34 weeks PMA; T2 = oral feeding initiation; T3 = discharge; T4 = 2 months CA

ii. Procedures

Figure 2. After informed consent is obtained, infants will be randomized into: Group 1 (M-MILK) and Group 2 (attention control). All data collection will be conducted in the same manner and at the planned time points for both groups. For all infants, we will collect infant characteristics, NISS, and family NICU activities daily ongoing from EPIC and self-report. All parents will receive an automatic daily text in the morning with a link to report their daily activities with infants when they come to the NICU. All parents are signing up for daily texts for up to 20 weeks to complete daily activities report every day during their participation. All parents will also receive a weekly phone call from a research nurse from enrollment until discharge. M-MILK is primarily implemented by nurses or parents. **At baseline (T0)**, we will conduct the EPDS assessment, and collect parent characteristics,

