buccal swab and fecal samples. For infants in the M-MILK group, the clinical team will place an order in EPIC for M-MILK to be provided starting on day 3 of life according to the M-MILK protocol. We will also schedule an in-person 30-minute M-MILK training session with parents in the M-MILK group, within 1 week of enrollment, provided by a research nurse. Parents in the M-MILK group are encouraged and supported to provide M-MILK when appropriate with the nurse's supervision. **At 34 weeks PMA (T1)**, we will collect PBQ, buccal swab and fecal samples. **At oral feeding initiation (T2)**, we will collect the EFS, and NCAST-Feeding video recording. Day of initiation of oral feeding is defined as the first of at least two consecutive days when the infant is able to orally consume $\geq 10\%$ of their prescribed feedings. Infants will be fed by nurses, speech therapist, or PI. We will implement the same feeding protocol, e.g., side-lying and swaddling during feeding. **During the week of planned discharge (T3)**, we will conduct EPDS, PSS: NICU, PDR, PBQ, Pumping and Breastfeeding, NMI, NAPI, and EFS assessments. We will collect NCAST-Feeding video recording, buccal swab and fecal samples. For the NCAST-Feeding video recording, both parents and infants will be recorded. Parents will also complete the M-MILK Acceptability Questionnaire at T3. For EFS and NAPI assessments, we will video record the assessments, when possible, to obtain videos for inter-rater reliability. **At 2 months CA (T4)**, we will send parents the fecal and buccal sample collection kits via USPS mail service. We will also conduct a phone/Zoom interview to complete the EPDS, PBQ, ASQ-3, and NeoEAT assessments. During the phone/Zoom interview, we will also provide parents instructions on how to collect buccal and fecal samples and securely send them back to us.

VIII. Safety Monitoring Plan

a. Potential Risk

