Strict confidentiality of data files will be maintained. Data management will be facilitated using REDCap. SAS (v 9.4) will be used for all statistical procedures and analyses. Levels of missingness, variable distributions, and outliers will be examined throughout data collection for quality assurance as well as prior to statistical modeling. We will calculate descriptive statistics for all variables of interest to describe the variability of study variables, and conduct sample size estimation for the planned R01 application. Comparisons will be made using an intent-to-treat approach with participants analyzed in the groups to which they were randomized. Feasibility will be assessed with respect to enrollment, adherence, acceptability, and safety. We will calculate the percentage of infants who (1) were eligible, approached, consented, enrolled, and randomized over the recruitment period, (2) were retained for the duration of the study, (3) completed all inpatient data collection, and (4) completed post-discharge follow-ups. To determine the adherence of M-MILK, we will calculate the daily numbers of completed M-MILK and the daily numbers of expected M-MILK implementation (numbers of hands-on care episodes before full gavage feedings) to obtain the daily percentage of M-MILK completion. We will summarize findings from M-MILK Acceptability Questionnaire by nurses and parents. We will also summarize findings from M-MILK EPIC charting regarding infant's responses and any adverse events to monitor for the safety of M-MILK.

X. Study Timeline

Table 2. The proposed pilot study will require 1 year to complete. During the first 3 months, we will hire and train the team members. We anticipate enrolling 2 infants per month for 9 months. An additional 3 months will be required to complete the intervention and collect study data. Data entry and analyses will be ongoing. We will spend 6 months to complete data analyses. An additional 6 months will be needed to prepare the final report and disseminations.

Table 2. Study Timeline

Activity/Month	Month 1-3	Month 3-12	Month 12-15	Month 15-21	Month 21-27
Preparation & Staff Training	X				
Recruitment & Enrollment		X			
Data Collection		X	X		
Data Entry & Analyses		X	X	X	
Final Reports & Dissemination				X	X

XIII. Literature Cited

1. Barfield WD. Public Health Implications of Very Preterm Birth. *Clin Perinatol*. Sep 2018;45(3):565-577.

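### Parent acceptability is asked only at discharge, with no form or reason taken at earlier exit, so the Aim 1 summary covers completers only and may overstate acceptability

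*Combined protocol and SAP*

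**What the plan says.** **Timing.** Section VII.a.vi, Table 1: "The M-MILK Acceptability Questionnaire will be completed by parents at discharge". The Procedures subsection agrees: "Parents will also complete the M-MILK Acceptability Questionnaire at T3", where T3 is the week of planned discharge. The form is not listed at baseline, 34 weeks PMA, oral feeding initiation or 2 months CA. For staff, Table 1 says "The nurses will complete the M-MILK Acceptability Questionnaire at the end of the entire study".

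**Role.** Section IV (Study Aims) makes acceptability part of Aim 1: "The M-MILK acceptability by nurses and parents will be determined via M-MILK Acceptability Questionnaire". It gives no score or percentage that would count as acceptable.

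**Analysis.** Section IX says "We will summarize findings from M-MILK Acceptability Questionnaire by nurses and parents". It gives no denominator and no rule for missing forms. Its intent-to-treat sentence is about comparisons between groups, not about this one-sample summary.

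**Exit before discharge.** Under Screening procedures (VII.a.ii), an enrolled infant who develops an exclusion criterion is excluded. Under Risks Related to Study Procedure (VIII.b.ii.1), an infant who becomes unstable or has a new diagnosis, and so no longer qualifies, is removed. Neither place mentions an acceptability form or a recorded reason for the family.

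**What else is reported.** Section IX also plans percentages for retention, inpatient completion and post-discharge completion, and a daily percentage of expected M-MILK administrations that were given.

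**Arm.** The Procedures sentence is not restricted to the M-MILK arm, and the same subsection says data collection is alike in both groups. The Attention Control Group section says control parents do not see the M-MILK content.

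**The concern.** A questionnaire given only at the end of the inpatient stay is answered only by families who are still there. If a family leaves because it dislikes M-MILK, its opinion is the one most relevant to acceptability, and the plan has no described way to collect it. With 6 or 10 families in the M-MILK arm, one missing opinion is a large share of the evidence.

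The opening summary says the pilot will inform the R01 application on feasibility and acceptability. A favourable summary among completers could be read there as the view of all families who were allocated to M-MILK. Once a family has left without being asked, the answer may not be recoverable.

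There is also a plain ambiguity. Read literally, control parents would rate an intervention they did not receive, and their answers could enter the same summary.

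**Working it through.** **1. The plan's own figures on how many families remain.** No acceptability figure is stated. The nearest stated figures are in VI.c (Sample): "We will enroll 12 preterm infants (6 per group"), then "Anticipated a 40% attrition rate", then a final sample of 12.

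- Retained = N × (1 − attrition) = 12 × 0.60 = 7.2, not 12.
- Enrolment needed to retain 12 = 12 / 0.60 = 20.

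The stated final sample does not follow from 12 enrolled. It does follow from the opening summary: "We propose the M-MILK pilot study (N = 20): a 2-group, 10 per group, parallel design". The two sizes conflict, so both 6 and 10 per arm are carried below.

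**2. Effect of an exit caused by M-MILK.** Let n be the families allocated to M-MILK, w the number who leave before T3 because they find M-MILK unacceptable, and a the number of T3 responders who find it acceptable.

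- Acceptability among responders = a / (n − w)
- Acceptability over all allocated, with the w exits counted as not accepting = a / n

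Suppose all responders accept, so a = n − w and the responder figure is 100%.

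| w | n = 6: a/n | gap (points) | n = 10: a/n | gap (points) |
|---|---|---|---|---|
| 0 | 6/6 = 100% | 0 | 10/10 = 100% | 0 |
| 1 | 5/6 = 83.3% | 16.7 | 9/10 = 90% | 10 |
| 2 | 4/6 = 66.7% | 33.3 | 8/10 = 80% | 20 |

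The documents do not give w; each row is an assumption. Reducing the questionnaire to accept or not accept is also an assumption, because the plan defines no such cut.

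**3. How likely is any loss before T3?** Section IV sets 90% as the target for inpatient completion. Take 10% as each family's chance of loss before T3, treat families as independent, and count one infant per family.

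- Expected losses: 6 × 0.10 = 0.6; 10 × 0.10 = 1.0.
- P(at least one loss) = 1 − 0.90ⁿ. For n = 6: 1 − 0.531 = 0.469. For n = 10: 1 − 0.349 = 0.651.

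These are losses from any cause. An infant who misses one inpatient item but whose parent still answers at T3 would count against the 90% without losing the form, so 10% is a rough guide.

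**4. Do the other outputs fill the gap?** Retention shows that a family left, but Section IX does not break it down by reason. Daily completion compares administrations given with those expected, and nurses or parents may give them, so it does not isolate a family's view. Neither shows whether M-MILK caused the exit.

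**The case against.** The strongest reply is that families who leave are not invisible. They lower the retention and inpatient completion percentages, and M-MILK that is not given lowers daily completion. An intervention that drove many families away should show as poor retention. This stands: a reader might infer that such families are never counted, and the documents do not support that. They are absent only from the questionnaire summary.

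Three further inferences should also be resisted.

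- *Parents who stop giving M-MILK are lost.* They are not, if they stay enrolled; they are still due the T3 form. Only leaving the study loses the answer.
- *The result is biased upward.* That requires exits before T3 caused by dislike of M-MILK. The exits the protocol describes are clinical, and such losses need not bias acceptability at all. Upward bias is plausible, not shown.
- *The 40% attrition figure measures the loss.* Section IV targets 90% completion for the inpatient phase against at least 50% after discharge, which suggests that most expected loss follows T3. The 40% also sits in a sentence that does not add up.

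It is also fair to say that asking nurses once, at study end, is a defensible choice. The documents give no turnover figure from which to judge the loss. Nor do they state a go or no-go rule on acceptability for the R01.

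What remains is narrow. No form or reason is described at early exit, and no denominator is defined.

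**Conclusion.** The point holds in this limited form. Followed as written, the plan summarises parent acceptability among families who reached discharge, and that summary may overstate acceptability among all families allocated to M-MILK.

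The possible size is material because the arm is small: up to 16.7 points (n = 6) or 10 points (n = 10) for a single exit caused by M-MILK, and zero if no exit has that cause. At the inpatient target, at least one loss of some kind has roughly an even chance or better (47% or 65%). The plan would give no means of telling whether that loss bears on acceptability.

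The restriction of the parent form to the M-MILK arm needs stating whatever the bias. This is a cheap improvement to a descriptive pilot measure and not a flaw that undermines the trial.

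**What to change.** 1. **Table 1 and Procedures.** Offer the existing questionnaire, with a recorded reason for leaving, to M-MILK-arm parents when the family withdraws or the infant is removed from the study, as well as at T3. State that control-arm parents do not complete it.
2. **Section IX.** Report parent acceptability over all families allocated to M-MILK. Show non-responders in the denominator, and add a worst-case bound that counts them as not accepting. This needs a short statement of which questionnaire result counts as accepting.
3. **Opening summary, Background, VI.a and VI.c.** Reconcile the 20 (10 per group) with the 12 (6 per group), and the 40% attrition with the final 12, so that the denominator is known.

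The cost is protocol wording, one short optional form at exit for at most 6 to 10 families, and a figure that may be less favourable. An extra administration at 34 weeks PMA and a different time for the nurse survey are optional; neither is needed to close this gap.
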